- Available recruitment methods (website, social media group) are listed in the spreadsheet **(Patient Recruitment/Contact Information.xlsx)**

2. Screening (Both UMass & Rutgers RA can perform)

- When a volunteer contacts us through AHHA lab's email or phone number, their **name**, **phone number**, and **email** will be collected using email reply (email) or pre-recorded voicemail instruction (phone).
 - UMass and Rutgers RAs will check the email and the voicemail box regularly (1 time a week by each RA). The following is an example.
 - Rutgers RA: Mon
 - UMass RA1: Wed
 - UMass RA2: Fri
 - RAs will **add a new record** in the RedCap and enter the volunteer's **name** in the **Name Data instrument**, and **phone number** and **email** in the **MCI Participant Demographics instrument** of the RedCap and remove processed voicemail messages.
 - The convention for naming the study ID for a person with MCI will be, for example, **MCI21 (password for Neuro-World administration is woorisoft!@)**
 - The prefix **MCI** followed by an incrementing **number** with 0 padding for a single-digit number (e.g., **MCI02** will be assigned after **MCI01**; **MCI22** will be assigned after **MCI21**).
 - The study ID will be used for a MCI participant. In other words, an active caregiver will not be given a separate study ID.
 - If a caregiver participates in the study, RAs will enter the caregiver's **name** in the **Name Data instrument**, and **phone number** and **email** in the **Caregiver Demographics instrument** of the RedCap and remove processed voicemail messages.
 - The caregiver for the person with MCI will be given a separate study ID, for example **CARE21**.
 - The prefix CARE followed by an incrementing number that matches that of the person with MCI. (record in the **Caregiver Demographics instrument**)

Logged in as [name] | Log out

My Projects

REDCap Messenger

Project Home and Design

- Project Home
- Project Setup
- Designer
- Dictionary
- Codebook

Project status: **Production**

Data Collection

- Record Status Dashboard
- Add / Edit Records**
- Study ID **MCI1**
- Select other record

Applications

- Project Dashboards
- Alerts & Notifications
- Calendar
- Data Exports, Reports, and Stats

Record Home Page

The grid below displays the form-by-form progress of data entered for the currently selected record. You may click on the colored status icons to access that form/event.

Choose action for record

Study ID MCI1

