Data Collection Instrument	Status
Volunteer Demographics	Incomplete
Screening Data	Incomplete (no data saved)
Randomization Form	Incomplete (no data saved)
Baseline Data	Incomplete (no data saved)
12-Week Follow-up Data	Incomplete (no data saved)
24-Week Follow-up Data	Incomplete (no data saved)

Legend for status icons:

- Incomplete (Red)
- Incomplete (no data saved) (Grey)
- Unverified (Yellow)
- Complete (Green)

- Any of the 3 RAs will call the volunteer, if the corresponding **Screening Data instrument** is not completed (i.e., not green), using the phone number in the **MCI Participant Demographics instrument**.
 - If the **volunteer** have approximately 30 minutes at the time of zoom call,
 - Each volunteer is asked for their demographic information, including gender, age, etc., which will be entered in the **MCI Participant Demographics instrument**.
 - If a caregiver participates in the study, each caregiver is asked for their demographic information, including gender, age, etc., which will be entered in the **Caregiver Demographics instrument**.

[figure not shown]
- Each volunteer is asked **inclusion and exclusion questions** (See [Appendix 2](#) for the inclusion & exclusion questions), answers of which will be entered in **the Screening Data instrument**.
- The volunteer's caregiver will be asked **inclusion and exclusion questions, the answers of which will be entered in the Screening Data instrument**. The fields are popped up when selecting 'Yes' to the questions 'Is a caregiver available to participate in this study'?
 - The volunteer, scoring MoCA 17 <= (score) < 26, will be included in our study.
- If both the volunteer and the active caregiver are eligible to join the study,
 - The RA will ask the **volunteer** and his/her active **caregiver** for their contact information, including their name, email address, and phone number if not collected yet, which will be entered in **the MCI Participant/Caregiver Demographics instrument**.
 - The RA will inform the volunteer and the active caregiver that the informed consent documents will be sent to them via email, and ask them to read, sign, and return the signed informed consent form.
 - The RA will change **the Form Status (Complete) field of the Screening Data** to Complete (i.e., green color). Green color indicates that the volunteer and the active caregiver are eligible for our study.
- If either the volunteer or the active caregiver or none of them is/are eligible to join the study,

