 - All the contact information (name, email, phone number) will be removed from **the MCI Participant/Caregiver Demographics instrument**.
 - The demographic information and the answers to the inclusion/exclusion question will be stored.
 - The RA will change **the Form Status (Complete) field of the Screening Data** to Incomplete (i.e., red color). Red color indicates that the volunteer and the active caregiver are not eligible for our study.
- If the **volunteer** or his/her have active **caregiver** do not have time at the moment,
 - The RA will schedule an appointment for a phone screening and enter the date and notes in **the Contact Attempt field of the Screening Data instrument**.
 - The RA leaves **the Form Status field of the Screening Data instrument** to Incomplete.
- If the volunteer cannot be reached,
 - The RA will leave a message.
 - Message: "*Hello. This is – from the UMass Amherst research team. I am contacting you about your interest in participating in our research about mild cognitive impairment. I'd like to discuss your eligibility to participate in our research. I would be grateful if you could call back us when you are available. My number is ----. Thank you.*"
 - The RA will enter the attempted date, time, and responses in **the Contact Attempt 1/2/3 for MCI Participant or Caregiver** in the **Screening Data instrument**.
 - If the RA completes the screening, enter the completed date, time, and their name in the **Screening Data instrument**.
 - If all the Contact Attempt 1/2/3 are entered, the RA will change **the Form Status (Complete) field of the Screened Result instrument** to Incomplete (i.e., red color).

- For those who are eligible to participate in the study (called *participants* hereafter), see the [3. Informed consent obtainment](#) and [5. Assessment at baseline](#) within the phone call.

3. Informed consent obtainment (Both UMass can perform)

- (When the RA, volunteer, and the active caregiver remain on the phone after the screening process) An RA will email informed consent forms either to 1) the volunteer and the active caregiver to their email addresses separately or 2) the active caregiver depending on the participants' preference.

- UMass and Rutgers RAs will email at the end of the **2. Screening** when both the volunteer and the active caregiver are determined eligible for our study.
- Use DocuSign @ [DocuSign Login - Enter email to start sign in](#).

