If you need help navigating technology (such as using Zoom or mobile apps), you can choose to have a friend or family member help you throughout this study. If you choose this option, they will be enrolled in the study with you. In that case, helpers need to 1) be 18 years or older, 2) understand your condition, and 3) can be contacted by the study team regularly. The person is not eligible if he/she 1) has been specifically hired to provide care for you and 2) has any impairments that prevent them from helping you.

Task

1. We will ask adults with MCI to do one of the following for the study (not both).

Group A: 1) We will ask you to play Neuro-World cognitive training games 30 minutes per day, twice a week for 12 weeks in your home setting. During this period, we will give you phone calls and ask if you adhere to the cognitive training and ask you to report the time of any additional cognitive and physical activities three times a week. 2) Upon completing 24 sessions, we will ask you to join online sessions (e.g., Zoom) to share your experience of using Neuro-World 3) Then, we will give you phone calls and ask if you have any significant changes in the level of daily activities for another 12 weeks and ask you to report the time of any additional cognitive and physical activities three times a week. This study lasts about six months, and you will spend about 27.2 hours in total.

Group B: 1) We will give you phone calls and ask if you have any significant changes in the level of daily activities for 12 weeks and ask you to report the time of any additional cognitive and physical activities three times a week. 2) After the 12 weeks, we will ask you to play Neuro-World cognitive training games 30 minutes per day, twice a week for 12 weeks in your home setting. During this period, they will give you phone calls and ask if you adhere to the cognitive training and ask you to report the time of any additional cognitive and physical activities three times a week. 3) Upon completing 24 sessions, we will ask you to join online sessions (e.g., Zoom) to share your experience of using Neuro-World. This study lasts about six months, and you will spend about 27.2 hours in total.

2. If helpers participate in the study, we will ask helpers to do the following for the study.

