2. Can you turn on/off a smartphone or a tablet computer? Can you start an application and use it on your smartphone or a tablet computer? It is ok to receive help from your caregiver on operating your smartphone or tablet computer.
3. Do you have access to a computer for online video communication (e.g., Zoom, Microsoft Team, Google Hangouts)?

The contacted researcher will ask the following questions regarding the exclusion criteria (5 minutes).

1. Do you have diagnosed neurologic or psychiatric disorders other than mild cognitive impairment?
2. Do you have a history of diagnosed traumatic brain injury?
3. Do you have hearing or vision impairment that can hinder you from playing games?
4. Do you have any significant impairment in your arm that could affect the use of a tablet computer?
5. Do you have diagnosed dementia with Lewy bodies, progressive supranuclear palsy, multiple system atrophy, or vascular parkinsonism?
6. Do you have diagnosed dementia?
7. Are you receiving any therapist-supervised cognitive training?

For Caregivers (optional)

The contacted researcher will ask the following questions regarding the inclusion/exclusion criteria (2 minutes).

Inclusion criteria

1. Are you 18 years old or older?
2. Do you know about your care receiver's health conditions?
3. Will you be willing to be contacted by the researchers on a regular basis in case your care receiver needs external help?

Exclusion criteria

4. Are you hired to provide care for your care receiver?
5. Do you have any cognitive, behavioral, or motor impairments that can affect assisting your care receiver in the study?

ATTENTION

When you open the box, CHECK if the following items are in the box.

1. One air-filled container
2. One tablet (in the air-filled container)
3. One tablet cover (a tablet is in the cover)
4. One charger (in the air-filled container)
5. One UPS return label

Please KEEP EVERYTHING you received that includes the following.

1. One outer box
2. One air-filled container
3. One tablet
4. One tablet cover
5. One charger
6. One UPS return label

Please DO NOT START cognitive training games until the researchers contact you.

When the study is complete, the researchers will contact and ask you to return all the items. At the time, you will need to do the following.

1. Place the tablet (with its cover) in the air-filled container.
2. Place the charger in the air-filled container.

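### Screening and consent steps are written for volunteer-caregiver pairs although the caregiver is optional, so an eligible volunteer with an ineligible helper is rejected and one with no helper has no clear route to randomisation

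*Protocol*

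**What the plan says.** Protocol Section 2 (Screening) gives two eligibility outcomes.

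- The first begins "If both the volunteer and the active caregiver are eligible to join the study". The record is set to green and consent follows.
- The second begins "If either the volunteer or the active caregiver or none of them is/are eligible to join the study". Here the protocol states "All the contact information (name, email, phone number) will be removed from" the participant and caregiver Demographics instruments. The record is set to red, and "Red color indicates that the volunteer and the active caregiver are not eligible for our study".

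Section 3 (Informed consent obtainment) repeats the joint condition: consent forms are emailed "when both the volunteer and the active caregiver are determined eligible for our study".

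Elsewhere the caregiver is optional. Section 2 itself says "If a caregiver participates in the study, RAs will enter the caregiver's" details, and it opens the caregiver screening fields only after a yes to whether a caregiver is available. The flyer tells volunteers "you can choose to have a friend or family member help you throughout this study". The caregiver questions in the screening questionnaire carry the label optional. Sections 5 and 8 mark the helper survey, calls and questionnaires as optional or conditional.

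**The concern.** The published criteria concern the volunteer: age, MCI, tablet use, access to video calls, and a list of exclusions. None requires a helper. The operating rule that turns those criteria into an enrolment decision does bring in the helper, and it lets the helper's ineligibility decide the volunteer's outcome.

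The document is a step-by-step procedure with colour codes and deletion instructions, and any of three research assistants at two sites may screen. One may follow the decision rule and another the optional wording. Enrolment could then depend on who makes the call.

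At stake are recruitment towards the stated 50 and the make-up of the sample. The flyer asks for adults who can use a tablet without help and offers a helper to those who need one for technology. The volunteers the flyer describes therefore have the least reason to bring a helper. They also matter most in a trial of self-administered training at home.

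**Working it through.** No formula applies. The check is to run each type of volunteer through the text and then follow the result to randomisation.

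**Step 1: the Section 2 branches.**

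| Volunteer | Helper | Result under Section 2 | Consistent with optional helper? |
|---|---|---|---|
| Eligible | Eligible | Green, consent follows | Yes |
| Eligible | Offered, but ineligible | Red, contact details removed | No |
| Eligible | None | Literal reading: red, details removed. Narrow reading (branches cover pairs only): no instruction | No on either reading |
| Ineligible | Any | Red, details removed | Yes |

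The second row needs no interpretation. Both the flyer and the screening questions rule out a helper who is hired to give care. A volunteer who meets every criterion, with a MoCA of at least 17 and below 26, but who offers such a helper falls into the red branch.

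**Step 2: from screening to randomisation.** Suppose the narrow reading is taken and a volunteer without a helper is not turned red. Sections 3 and 4 still contain these conditions:

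1. The consent email is triggered when both people are eligible.
2. The branch for proceeding at once requires both to have time.
3. A separate consent call assumes that the caregiver is with the volunteer.
4. In both call scenarios, the Informed Consent form is set to complete once volunteer and caregiver have signed.
5. The baseline visit is booked when the caregiver is also free for 2 hours. In the separate-call scenario the same sentence first calls the caregiver's attendance optional and then lists the caregiver among those who must be available.
6. Section 4 assigns a group once the Informed Consent form is complete.

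A volunteer with no enrolled helper cannot meet items 1 and 4 as written, and item 6 depends on item 4.

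**Step 3: what is removed.** The deletion rule covers the Demographics instruments, where Section 2 stores phone and email. Section 2 stores the name in a separate Name Data instrument, which the rule does not mention.

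**Step 4: size.** The number of otherwise eligible volunteers needed to enrol 50 would be 50 / (1 − p), where p is the share without an eligible helper. The documents give no value or range for p, so no figure is offered.

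**The case against.** The strongest reply is that the document should be read as a whole. Caregiver fields open only when a caregiver is available, and the optional wording recurs in many sections. On that reading the two branches cover only pairs in which a helper was offered, and the volunteer without a helper is an omitted case, not a rejected one. This is a fair reading, and it limits the point. A reader might infer that the plan excludes people who live alone or manage technology by themselves, or that it has become a trial of pairs. The documents do not establish that, because it follows from only one of two readings. What remains is that the volunteer with an ineligible helper is rejected on either reading, and the volunteer without a helper cannot satisfy Section 3 as written.

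A second reply concerns permanence. It is tempting to say that a wrongly rejected volunteer is lost for good. The documents do not support that. The name may remain in the Name Data instrument, nothing calls for deleting a volunteer's emails to the lab, and the volunteer may name another helper on the call or make contact again. Removing phone and email makes correction harder but not impossible.

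A third reply is that the conflict acts before randomisation and does not bias the paired comparison of periods in SAP Section 2. That is correct. The effect is on recruitment and on whom the result describes.

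**Conclusion.** The conflict is real and lies within the protocol. Sections 2 and 3 contain joint conditions that contradict the caregiver's optional status in the rest of the document. For an eligible volunteer with an ineligible helper, the rule is wrong as written. For an eligible volunteer with no helper, it either rejects or gives no instruction, and the consent conditions block the route to randomisation.

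The consequences are conditional on the text being followed literally: slower recruitment towards 50 and a sample tilted towards volunteer-caregiver pairs. Their size cannot be derived from the documents. A reader might also infer that eligible people have already been turned away; nothing in the documents shows this. The text should be corrected. If screening has already taken place, the sponsor should state which rule was applied.

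**What to change.** Reconcile Sections 2 and 3 with the optional status stated elsewhere:

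1. In Section 2, decide the volunteer's eligibility from the volunteer's own criteria and MoCA. Let the helper's eligibility decide only whether that helper is enrolled.
2. Add an explicit branch for an eligible volunteer with no helper or an ineligible one. Include the option to name another helper. This matters where the volunteer relies on help to operate the device, which question 2 of the volunteer's inclusion questions allows.
3. Remove a volunteer's contact details only when the volunteer is ineligible.
4. In Section 3, make each joint condition apply only when a helper is enrolled: the email trigger, both having time, the accompanying caregiver, the second signature and the 2-hour availability.

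The cost is a few lines of text. The one downside is that fewer participants will have helper-reported data.

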- If both the volunteer and the active caregiver have time,
 - The RA will give the volunteer and the active caregiver to read the informed consent form.
 - The RA will answer questions should the volunteer and the active caregiver have any.
 - When the volunteer and the active caregiver sign (using **DocuSign**) and return the signed informed consent form,
 - The RA will enter the date the forms are received.
 - The RA will change **the Form Status field of the Informed Consent instrument** to Complete.
 - The signed informed consent will be stored in the UMass-supported cloud (i.e., OneDrive).
 - The RA will schedule an assessment with the volunteer and the active caregiver for the baseline assessment when one UMass RA, the Rutgers RA, the volunteer, and the active caregiver are available for 2 hours in a row (AHHA lab account, [contact]).
 - The RA will mark the scheduled assessment on the Google calendar.

- If the volunteer or the active caregiver do not have time,
 - The RA will schedule an appointment when any of the RAs are available based on the Google calendar (AHHA lab account, [contact]).
 - The RA will inform other RAs of the scheduled appointment in the Slack channel.

- (When an RA is making a separate call) An RA, who is available at the scheduled appointment time, will call the volunteer, assuming that the active caregiver accompanies the volunteer.

- The RA will give the volunteer and the active caregiver time to read the informed consent form.

- The RA will answer questions should the volunteer or the active caregiver have any.
- When the volunteer and the active caregiver sign and return the signed informed consent form,
 - The RA will enter the date the forms are received.
 - The RA will change **the Form Status field of the Informed Consent instrument** to Complete.
 - The signed informed consent will be stored in the UMass-supported cloud (i.e., OneDrive).
 - The RA will schedule an assessment with the volunteer (optionally, and the active caregiver) for the baseline assessment when one UMass RA, the Rutgers RA, the volunteer, and the active caregiver are available for 2 hours in a row (AHHA lab account, [contact]).
 - The RA will mark the scheduled assessment on the Google calendar.

4. Random assignment into two groups (Only UMass RA can perform)

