- When the UMass RA finds a study ID with the completed **Informed Consent instrument** (i.e., green color), the RA refers to **random_group_assign.xlsx** (in the Google folder **Pre-determined randomization, which is only available to the UMass RAs**) and assigns the study ID to either Group A or B.

- **Group A**
 - First period: Neuro-World game intervention (12 weeks)
 - Second period: phone interaction + usual care (12 weeks)
- **Group B**
 - First period: phone interaction + usual care (12 weeks)
 - Second period: Neuro-World game intervention (12 weeks)

- **The Randomization instrument** will be hidden from the Rutgers personnel throughout the study.

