
Highest level privileges:
 
Project Design and Setup 
 
User Rights 
 
Data Access Groups 
 
Privileges for data exports (including PDFs and API exports), reports, and stats:
 
Data Exports
 
* De-identified means that all free-form text fields will be removed, as well as any date/time fields and Identifier fields.
 
No Access 
 
De-Identified* 
 
Remove all tagged Identifier fields 
 
Full Data Set 
 
Add/Edit/Organize Reports 
 
Also allows user to view ALL
	
This privilege has no effect on data imports or data exports.
 

	No Access (Hidden)	Read Only	View & Edit	

Volunteer Demographics				

Screening Data				

Screened Result				

Informed Consent				

Randomization Form				

Baseline Data				

12-Week Follow-up Data				

24-Week Follow-up Data				

		No Access (Hidden)	Read Only	View & Edit	Volunteer Demographics				Screening Data				Screened Result				Informed Consent				Randomization Form				Baseline Data				12-Week Follow-up Data				24-Week Follow-up Data			

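### The UMass RAs who recruit, screen and take consent can open the allocation list, so the written procedure does not ensure allocation concealment for the volunteers they handle

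*Protocol*

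**What the plan says.** **Access to the list.** Protocol section 4 has a UMass RA look up the group in random_group_assign.xlsx, kept in a Google folder labelled "Pre-determined randomization, which is only available to the UMass RAs". The trigger is a completed consent form: "When the UMass RA finds a study ID with the completed" consent instrument, the RA consults the file and assigns Group A (game first) or Group B (game second).

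**Who enrols.** The role table at the start of the protocol marks UMass RAs for recruitment, screening, consent and random assignment. It marks Rutgers RAs for the first three but not for assignment. In section 2, "Any of the 3 RAs will call the volunteer" when screening is incomplete. The heading "3. Informed consent obtainment (Both UMass can perform" names UMass for consent, although the role table marks both sites.

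**Eligibility.** Appendix 2 is a set of yes/no questions. Section 2 adds a score rule: "The volunteer, scoring MoCA 17 <= (score) < 26, will be included in our study".

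**Study IDs.** Numbers increment and are given when the volunteer's record is created, before screening (the paragraph beginning "The convention for naming the study ID for a person with MCI will be, for example").

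**Masking.** The randomization form is hidden from Rutgers personnel, and the meeting scripts ask participants not to reveal their group to the Rutgers assessor.

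**Analysis.** SAP section 2 plans paired t-tests of intervention against non-intervention periods, one-sided at 0.05. It mentions no period or sequence term.

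**The concern.** Concealment means that whoever decides on a volunteer's entry cannot know the next assignment. Here the enrolling staff at UMass have the whole list. The safeguards that are described serve another purpose: hiding the form from Rutgers protects outcome scoring, not enrolment.

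If foreknowledge, deliberate or not, changes which volunteers enter each sequence, Groups A and B may differ in how they would have changed without the game, for example through retest gain. A paired comparison pooled over both groups removes such changes only if they are alike in the two sequences. A period term in the analysis would not repair a difference between them.

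**Working it through.** **1. Setting the sections side by side.** The role table and sections 2 to 4 give UMass RAs both the enrolment decisions and the list. Section 4 orders the steps correctly (consent, then look-up). The supplied text describes no separate list holder, locked rows, one-at-a-time release, or split between the RA who enrols and the RA who assigns.

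**2. What foreknowledge could affect.** The layout of the file is not described, so there are two alternatives, and they do not add together.

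- *List keyed to study ID.* The group is fixed when the ID is given, at first contact. Appointment timing cannot change it. Only exclusion, discouragement or contact effort (section 2 allows up to three logged attempts) could be affected.
- *List used in order.* The ID does not give the row, because IDs also go to volunteers who later prove ineligible. The next open row is visible, and the timing or order of assignment could be affected. RAs book the consent appointments ("The RA will schedule an appointment when any of the RAs are available based on the Google calendar"), and the order in which completed consents are taken to the list is not stated.

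**3. How an imbalance would reach the estimate.** Let D be the change in the game period minus the change in the control period, τ the true effect, and π the untreated period-2 change minus the untreated period-1 change. Leave carry-over aside.

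- Group A: mean D = τ − π_A
- Group B: mean D = τ + π_B
- With 25 per group, the pooled mean is τ + (π_B − π_A)/2.

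A period-adjusted estimate averages the two group means, so at 25/25 it has the same bias.

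**4. Illustration.** From the documents: N = 50 and a one-sided test at 0.05 (49 degrees of freedom). Everything else is assumed, because the supplied text gives no allocation ratio, SD, retest gain or rate of steering: 25 per group; 15 volunteers in A and 10 in B of a type whose first-period retest gain is g MoCA points larger; D normal within type.

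- π_A = −(15/25)g = −0.6g
- π_B = −(10/25)g = −0.4g
- Bias = (−0.4g + 0.6g)/2 = 0.10g, that is 0.05, 0.10 and 0.20 points for g = 0.5, 1 and 2.

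Simulated one-sided error with τ = 0 (400,000 runs per cell; repeat runs agreed within 0.002):

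| Split A v B | SD of D | g = 0.5 | g = 1 | g = 2 |
|---|---|---|---|---|
| 15 v 10 | 2 | 0.068 | 0.083 | 0.095 |
| 15 v 10 | 3 | 0.062 | 0.073 | 0.089 |
| 15 v 10 | 4 | 0.059 | 0.068 | 0.081 |
| 14 v 11 | 3 | 0.057 | 0.061 | 0.063 |
| 13 v 12 | 3 | 0.051 | 0.050 | 0.042 |
| 10 v 15 | 3 | 0.038 | 0.027 | 0.011 |
| Concealed, averaged over chance splits | 3 | 0.049 | 0.048 | 0.042 |

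The SD range may be too low. D equals ±(2 × week 12 − baseline − week 24), so with independent visit errors of SD s its SD is √6 × s = 2.45s. SDs of 2 to 4 then imply only 0.8 to 1.6 points per visit. At SD 6 (2.4 per visit), 15 v 10 with g = 1 gives about 0.06.

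A split of 15 v 10 or more extreme arises by chance with probability 0.129 in each direction (0.258 in total) under perfect concealment. The 15 v 10 rows are therefore conditional on one split, while the last row is an average over splits.

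**The case against.** The strongest reply is that the design leaves foreknowledge little to work on. Each participant receives both conditions, the Appendix 2 questions are largely factual, and the Rutgers assessor is kept from the allocation. The Rutgers RA also screens, without access to the list, so not every volunteer is exposed. All of this stands, and it limits the expected harm. It does not supply concealment.

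A reader might infer more than the documents support, in four ways:

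- *That assignments were in fact foreseen or steered.* Nothing shows this. Row locking or a division of duties among UMass RAs may exist unwritten, and the SAP text available begins at its section 1.
- *That sequential IDs reveal the group however the list is used.* They do so only if the list is keyed to ID. Control over timing matters only if it is not.
- *That UMass RAs can tilt entry through MoCA scoring.* Section 2 states the range but not who scores the screening MoCA. Appendix 2 contains no MoCA, and the MoCA administrations that are described are by the Rutgers RA. The section 2 heading lets either site screen, so this is possible but not established.
- *That the test's true error is about 7%.* That figure belongs to one assumed split. RAs cannot see retest gain and could act only on what screening shows, which may be unrelated to it. The opposite split makes the test conservative.

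**Conclusion.** The point holds as a gap in the written procedure: staff who recruit, screen and take consent at UMass can open the list, so concealment is not ensured for the volunteers they handle. That conclusion rests on the text alone and needs no assumed number.

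The consequence is probably small. Under the assumed 15 v 10 split, the bias is 0.05 to 0.20 MoCA points and the one-sided error is 0.059 to 0.095 over SDs of 2 to 4. It shrinks with a larger SD or a milder split, and its direction is unknown. These figures show that the crossover does not make the bias impossible; they do not estimate what happened. The change is worth making because it is cheap and because reanalysis cannot restore concealment afterwards.

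**What to change.** **Remaining enrolments.** Remove random_group_assign.xlsx from the enrolling RAs' access. Have an existing team member who does not screen, consent or assess hold it (for example an investigator, if that description fits), or use a concealed REDCap randomization function if one is available. Release one assignment at a time, in order of consent, once eligibility and consent are locked. Release can stay before baseline, so the meeting scripts and tablet shipping need not change.

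**Participants already allocated.** State whether the list was used by study ID or in order, and by whom, and report baseline characteristics by sequence. The documents do not give enrolment status; if recruitment has ended, this is the only part that still applies.

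**Cost.** One change of file access, some time from the list holder and a short wait per release; for those already allocated, one sentence and one table. No extra visits or participants are needed.
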